Carbohydrates can be ingested in the form of complex structures, such as polysaccharides containing very long carbohydrate chains (starch), as well as simpler structures, such as disaccharides (lactose, sucrose, maltose and trehalose) and monosaccharides (glucose, galactose and fructose) (McQuilken, 2021).

The digestion of this macronutrient is achieved in two stages, the first corresponds to the intraluminal phase, which is mediated by salivary and pancreatic amylase, and the second, by the mucosal phase where an interaction with the apical surface

of the enterocyte occurs (de Koning et al., 2020). Regarding the luminal phase, this begins in the mouth where carbohydrates begin to be assimilated by the reaction carried out by the enzyme α -amylase, or also known as ptyalin, which is produced by the salivary glands, in order to hydrolyze the α (1,4) bonds of linear glucose polymers, obtaining as a product smaller oligomers, such as maltose, maltotriose and α -limit dextrins (Sanders, 2016). It should be emphasized that this enzyme leaves intact α -bonds (1,6), α -terminal bonds (1,4) and also those that are close to branch points. In addition, α -amylase is usually inactivated by the modification of gastric juices on the pH of the stomach, so that carbohydrate digestion is incomplete, continuing until it reaches the small intestine.

As the pH of the chyme is neutralized in the small intestine by the action of bicarbonate, pancreatic α -amylase begins to be released to continue the chemical digestion of carbohydrates.

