The products of the previous reactions carried out by the salivary and pancreatic α -amylase enzymes are again hydrolyzed on the apical surface of the enterocytes, although this time the enzyme complexes responsible are glucoamylase, saccharase-isomaltase and glucosidases. Glucoamylase goes on to hydrolyze the α (1,4) bonds at the non-reducing end of maltotriose and α -limiting dextrins, resulting in glucose and isomaltose monomers. The latter is not able to be hydrolyzed by this enzyme due to its inability to break α (1,6) bonds, giving rise to the saccharase-isomaltase enzyme, which is divided into 2 subunits, one of which is saccharase-maltase, responsible for catalyzing the digestion of sucrose and maltose, obtaining as product the monosaccharides that compose it; and the second subunit isomaltase-maltase, in charge of digesting isomaltose and maltose. And finally, there are the enzymes α and β Glucosidase, the first catalyzes the hydrolysis of terminal α -linked D-glucose residues (1,4) next to the non-reducing ends, thus releasing β -glucose. It should be noted that this enzyme is capable of hydrolyzing α (1,6) linkages, thus marking the end of the digestion of the macronutrient of interest. On the other hand, the enzyme β -Glucosidase is responsible for catalyzing the hydrolysis of the β (1,4) linkage of lactose, to obtain glucose and galactose, as well as breaking down glycolipids, obtaining a monosaccharide, such as glucose or galactose, and ceramide (Sanders, 2016).

Regulation of plasma glucose levels.

As a consequence of food consumption, blood glucose levels rise in response to carbohydrate consumption, which is influenced by the type of carbohydrate, the elimination of glucose from the bloodstream and the interaction with other food components (Sanders, 2016), so control systems are required to detect these changes in order to maintain blood glucose within normal values. Some of these

processes is the secretion of insulin and glucagon, these mechanisms are synchronized which allows maintaining stable blood glucose levels during the interprandial period (Pinés Corrales et al., 2020).

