The concept of the glycemic index has been expanded over the years, giving rise to mathematical products such as the glycemic load (GL), which is defined as the quantity and quality of carbohydrates consumed and estimates the total glycemic effect of the diet, for its obtaining it is necessary to multiply the amount of CHO contained in the food ingested by the GI value ($GL = GI \times \text{available carbohydrates}$).

The increase to the glycemic load is associated with an unfavorable physiological response, mainly for people living with diabetes, since blood glucose and insulin values rise sharply. Foods with $GL \leq 10$ are considered low GL and foods with $GL \geq 20$ are considered high GL.

OBJECTIVES

General objective

To evaluate the *in vivo* bioavailability of bioactive compounds from a *H. sabdariffa* beverage and their immunomodulatory potential against moderate inflammation caused by SARS-CoV2 as well as enzymatic inhibition of α -amylase and α -glucosidase enzymes *in vitro*.

Specific objectives

1. To perform HPLC-DAD-MS characterization of a *Hibiscus sabdariffa* hibiscus-based beverage.
2. To perform an acute single-blind clinical trial, administering a hibiscus drink to normal-weight adults.
3. To evaluate the bioavailability of organic acids and phenolic compounds in urine and plasma samples present in the *H. sabdariffa* beverage.
4. To evaluate the immunomodulatory potential of the metabolites identified as bioavailable in plasma samples.
5. To evaluate the enzymatic inhibition of α -amylase and α -glucosidase exerted by the digested, placebo and treatment beverages.
6. To evaluate the *in vivo* GR and IR of the placebo beverage and treatment beverage.

. GENERAL METHODOLOGY

First Stage

Obtaining hibiscus-based beverage and placebo.

The hibiscus-based beverages (H.sabdariffa) and placebo were obtained from the reformulated company NUTRIYÉ SAPI de CV, located in the city of Guadalajara, Jalisco, Mexico.

Participants.

Twelve normo-weight volunteer participants without any medical condition were included. The invitation to participate was made through ITESO's communications office, as well as through announcements in social networks. They were selected according to the following criteria:

Within the inclusion criteria to be considered are those mentioned in Table 4.2.

Table 4.2. Non-inclusion and inclusion criteria for volunteer selection.

Inclusion criteria		Non-inclusion criteria	

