Samples will be subjected to an in vitro digestion model adapted from the methodology by Blancas-Benitez et al., (2018). First, the samples will be subjected to an enzymatic hydrolysis process with pepsin at a temperature of 37°C for 1 h (step 1); the phenolic compounds (FC) released in the supernatant at this stage are considered as the FC present in the gastric fraction (GasF). Subsequently, the samples are hydrolyzed with pancreatin 5 mg/ml, P-1750, Sigma Aldrich) and α -amylase (120 mg/ml, A-6255, Sigma Aldrich) (step 2). The CF released at this stage of digestion is considered the CF present in the intestinal fraction (IntF).

α -amylase activity.

The products obtained from the various stages of sample digestion will be used to determine the α -amylase enzyme activity (U/mL) using the kinetic method proposed in the specifications of the amylase activity assay kit (Sigma-Aldrich #MAK009), which consists of taking an aliquot of 50 μ L of the various samples and depositing them in a 96-well plate, then mixed with 100 μ L of master solution, previously prepared with 50 μ L of amylase assay buffer and 50 μ L of α -amylase substrate mixture, then incubated at 25°C and at minute 3, the absorbance at 405 nm is measured to obtain the initial time (T-initial) using the Synergy HT microplate reader (Biotek Instruments, Inc. , USA), readings will be taken every 5 min until the values of the samples approach that obtained at the highest concentration of the standard (20 nM/well) giving rise to the T-final. A calibration curve will be performed with Nitrophenol at concentrations of 4, 8, 12, 16 and 20 nM/well. One enzyme unit is the amount of amylase that cleaves ethylidene-pNP-G7 to generate 1 mM p-Nitrophenol per min. The enzyme activity will be expressed as percentage inhibition (I%) and determined with the equation (Eq 6.1):

$$I\% = \frac{(B \times \text{Factor de dilución})}{\text{Tiempo de reacción} \times V} \quad \text{Ec 4.1}$$

Where:

B refers to the amount of Nitrophenol generated, reaction time is the T-final minus T-initial in minutes and V denotes the volume of sample added to the well (μ L).

α -glucosidase activity.

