The inhibition of α -glucosidase of the beverages will be evaluated using the products of the different phases of the in vitro digestion and will follow the methodology described in the specifications of the α -glucosidase kit (Sigma-Aldrich #MAK123) where first 220 μ L of deionized water will be placed in a well of a reading plate and in another well 20 μ L of deionized water will be placed and 200 μ L of calibrator will be added to one of them. From the samples previously prepared in 50 mM phosphate buffer (pH 7.0) 20 μ L will be taken and placed in separate wells and 200 μ L of master solution will be transferred to each of them, the solution will be previously prepared with 200 μ L of p-nitrophenyl- α -D-glucopyranoside (NPG) buffer and 8 μ L of NPG substrate, then incubated at 37° C and absorbance will be measured at 405 nm using Synergy HT microplate reader

(Biotek Instruments, Inc., USA), the initial measurement (T-initial) will be read and after 20 minutes the final absorbance (T-final) will be taken.

The enzyme activity will be expressed in units per liter (unt/L) and calculated with the equation (Eq 6.2) where one enzyme unit is the amount of α -glucosidase that catalyzes the hydrolysis of 1 mM p -nitrophenyl- α -D-glucopyranoside per minute at pH 7.0.

$$\text{unt/L} = \frac{(\text{Abs final} - \text{Abs inicial})}{\text{Abs del calibrador} - \text{Abs del agua}} \times 250 \text{ unt/L} \quad \text{Ec 4.2}$$

Where:

Abs of the calibrator is the value for the calibrator at 20 minutes, Abs of the water represents the value of the water at 20 minutes and unt are units.

Evaluation of glycemic response.

To obtain the biological sample, a lancet will be used to puncture the thumb of the volunteer's finger and the sample will be collected on highly sensitive test strips for capillary glucose measurement of the OneTouch Ultra® System.

The portable system used for pre- and postprandial glucose measurement allows the monitoring of capillary glycemic response under experimental conditions for healthy subjects. With the use of this equipment, measurements will be obtained from t_0 (preprandial), and at 15, 30, 45, 60, 90 and 120 min (postprandial). The results will be expressed in mg/dL.

Insulin analysis.

Participants will be required to hold a hand warmer ($\sim 40^\circ\text{C}$) for 5 min before each capillary blood sampling, to stimulate peripheral blood flow.

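### No described step supplies α-glucosidase to the α-glucosidase assay, and the α-amylase assay has no uninhibited reference, so percentage inhibition (objective 5) cannot be obtained as written

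*Combined protocol and SAP*

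**What the plan says.** Specific objective 5 is to evaluate inhibition of α-amylase and α-glucosidase "exerted by the digested, placebo and treatment beverages". The general objective also includes this in vitro inhibition, and Expected Results names it among the possible mechanisms of the hypoglycemic effect.

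Under *In vitro gastrointestinal digestion of the beverages*, the gastric step reads "the samples will be subjected to an enzymatic hydrolysis process with pepsin at a temperature of 37°C for 1 h (step 1"). The intestinal step reads "Subsequently, the samples are hydrolyzed with pancreatin 5 mg/ml, P-1750, Sigma Aldrich") and adds "amylase (120 mg/ml, A-6255, Sigma Aldrich) (step 2"). No other enzyme is named.

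Under *α-amylase activity*, 50 µL of digest is mixed with 100 µL of master solution (50 µL assay buffer and 50 µL substrate mixture). The result is labelled percentage inhibition and calculated with Ec 4.1.

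Under *α-glucosidase activity*, inhibition "of the beverages will be evaluated using the products of the different phases of the in vitro digestion". Each sample well receives 20 µL of sample, then 200 µL of "master solution will be transferred to each of them, the solution will be previously prepared with" 200 µL of NPG buffer and 8 µL of NPG substrate. The only other wells are water and calibrator. The result is activity in units per liter (Ec 4.2).

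**The concern.** An inhibition assay needs a known amount of the target enzyme, the candidate inhibitor, and the same enzyme without the inhibitor to define 0%. Both procedures instead put digest into a kit that measures whatever activity the sample already contains.

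For α-glucosidase, the described steps include neither the enzyme nor an uninhibited reference. The protocol's own account of carbohydrate digestion places the glucosidases after the amylase stage, where the products "are again hydrolyzed on the apical surface of the enterocytes". This in vitro model has no such surface. For α-amylase, the only named enzyme is the one used to digest the sample, and no digest without beverage is planned.

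At stake is whether the laboratory data can answer objective 5 and support enzyme inhibition as a mechanism. A low glucosidase reading in both drinks could not be told apart from strong inhibition, no inhibition, or simple absence of enzyme.

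**Working it through.** The plan states no figure to reproduce. The check lists what is in each well and then evaluates the two equations.

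**1. Named enzyme sources**

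| Assay and fraction | Enzymes from digestion | Target enzyme added in assay | Uninhibited reference |
|---|---|---|---|
| α-glucosidase, gastric | pepsin | none | none |
| α-glucosidase, intestinal | pepsin, pancreatin, α-amylase | none | none |
| α-amylase, gastric | pepsin | none | none |
| α-amylase, intestinal | pepsin, pancreatin, α-amylase | none | none |

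Only the last row has a named target enzyme in contact with the beverage.

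**2. α-glucosidase, Ec 4.2:** units/L = (Abs final − Abs initial) / (Abs calibrator − Abs water) × 250.
The following absorbances are assumed for illustration: initial 0.10, calibrator 1.00, water 0.05.
- No enzyme in the well, so the absorbance change is 0 and the result is 0 / 0.95 × 250 = 0 units/L. It is the same at true inhibition of 0%, 50% and 100%.
- A fixed enzyme amount giving a change of 0.40 when uninhibited: 0.40 / 0.95 × 250 = 105.3 units/L at 0% inhibition, 0.20 / 0.95 × 250 = 52.6 at 50%, and 0 at 100%.

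The equation can carry the information, but only once enzyme is present.

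**3. α-amylase, Ec 4.1:** B × dilution factor / (reaction time × V).
V = 50 µL is from the protocol. Assumed values are B = 20 when uninhibited, time 20 min and dilution factor 1.
- Gastric fraction with no amylase: B = 0, result 0 for either drink.
- Intestinal fraction, uninhibited: 20 / (20 × 50) = 0.020. At 25%, 50%, 75% and 100% inhibition it is 0.015, 0.010, 0.005 and 0.

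So the intestinal reading does respond to inhibition. It is a rate, however, with no reference term, and the number labelled as inhibition falls as inhibition rises.

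**4. What a treatment/placebo ratio can and cannot show.** Suppose treatment inhibits 50% and placebo 0%: the ratio is 0.010 / 0.020 = 0.5. Suppose treatment inhibits 75% and placebo 50%: the ratio is 0.005 / 0.010 = 0.5. The ratio shows that treatment inhibits more than placebo, but it does not give the inhibition by either drink.

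**5. With a beverage-free reference.** I% = 100 × (1 − activity with beverage / activity of beverage-free digest). Readings of 0.020, 0.015, 0.010, 0.005 and 0 against a reference of 0.020 return 0%, 25%, 50%, 75% and 100%.

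**The case against.** Several points can fairly be made for the plan.

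- **A reader might infer that neither assay can measure inhibition at all.** That is too strong for intestinal amylase. Step 2 puts α-amylase in contact with the beverage, and with equal enzyme dose and dilution, lower residual activity with treatment than with placebo is evidence of relative inhibition. This objection stands.
- **The kit specifications, or glucosidase in pancreatin, may supply the missing enzyme.** Neither the specifications nor the composition of pancreatin is in the documents, so a reading of exactly zero in every fraction cannot be asserted. But the section writes out the assay steps and lists no enzyme. A trace from pancreatin would be of unknown amount, would have no uninhibited reference, and would not reach the pepsin-only fraction.
- **A reader might blame acid pH**, since the background says that α-amylase "is usually inactivated by the modification of gastric juices on the pH of the stomach". That sentence describes digestion in the stomach, and the text goes on to neutralisation in the small intestine. The plan adds amylase after the pepsin step and uses assay buffer, and no digest pH is given. The pH reading is not supported.
- **A reader might infer that the amylase dose forces a dilution that removes any hibiscus effect.** The 120 mg/ml may be a stock concentration, and neither the final volume nor the specific activity is given. Ec 4.1 already allows for a dilution factor. No dilution figure can be derived.
- **This is bench work.** That is correct: no participant procedure or outcome depends on it.

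**Conclusion.** The concern holds in a limited form. As written, the α-glucosidase assay cannot show inhibition by the beverages in any fraction, because it reads only whatever uncontrolled activity is in the digest. The α-amylase assay gives no information on inhibition in the gastric fraction, where no amylase is named. In the intestinal fraction it gives at most a relative treatment-versus-placebo comparison, provided enzyme dose and dilution are equal. Percentage inhibition is not obtainable from either assay.

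This rests on the steps the protocol writes out. It would change for α-glucosidase if a kit step not reproduced there adds a fixed amount of enzyme and an enzyme-only control. The absorbances, B and reaction time used above are illustrative; the conclusions do not depend on their values.

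The consequence is confined to objective 5 and the enzyme-inhibition part of the general objective. A reader might infer that the glucose, insulin, cytokine or bioavailability results are compromised. They are measured separately and are not. Nor does the point remove all support for the hypoglycemic hypothesis: Expected Results lists enzyme inhibition as one possible mechanism, and the background cites earlier inhibition data.

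**What to change.** Amend the two assay sections before the assays are run; both are written in the future tense.

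1. **Add target enzyme where none is named.** In the α-glucosidase assay (all fractions) and the α-amylase assay of the gastric fraction, add the same known amount of target enzyme to every well with the digest, at the assay pH, before the substrate.
2. **Add a 0% reference to both assays.** Take a beverage-free digest (same reagents, water in place of beverage) through the same steps.
3. **Add a background well.** Use the matching digest without added target enzyme. For intestinal amylase the target is the step 2 enzyme, so the background is a digest prepared without that enzyme.
4. **Intestinal amylase.** Use and record the same step 2 enzyme dose and the same dilution for treatment, placebo and the beverage-free digest. Removing and re-adding enzyme is not required.
5. **Report** inhibition as 100 × (1 − activity with beverage / activity of beverage-free digest), with both activities background-corrected, and compare hibiscus with placebo on that scale.

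If the kit procedure already includes an enzyme addition and control, state them in the protocol. The cost is the purchase of enzyme and a few extra wells per plate; no participant is involved.

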Hibiscus sabdariffa L., also known as roselle, karkadé, rosa de jamaica, among other names, is an herbaceous medicinal plant, which in Mexico is better known as jamaica. It is an annual cultivated shrub that belongs to the Malvaceae family (Duarte-Valenzuela et al., 2016), and grows to a maximum height of 3 m, with tri- or pentalobed leaves about 15 cm long, alternating on the stem. Its flowers measure 8 to 10 cm in diameter, are red at the base and pale at the ends, while the calyx is deep red, fleshy and rich in malic acid (Secretaría de Agricultura y Desarrollo Rural, 2021). In Mexico, hibiscus calyxes are used in the preparation of a refreshing drink widely consumed by the population, which gives it both economic and cultural importance (Duarte-Valenzuela et al., 2016), however, according to national production is insufficient and at least 50% of the hibiscus consumed is imported.

In Latin America it is used as a food and source of dietary fiber (Da-Costa-Rocha et al., 2014). Despite being native to Asia, it is also cultivated in many areas, including Central America and Africa. This species is usually cultivated for its fibers and calyxes, and includes three different genotypes: green, red which is the most commonly used type) and dark red (Andzi Barhé & Feuya Tchouya, 2016). Hibiscus calyxes have been recognized as a source of dietary fiber (DF) with antioxidant activity (Sayago-Ayerdi & Goñi, 2010) as well as anti-hypertensive, anti-hypercholesterolemic and anticarcinogenic effects (Lin et al., 2012).

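### Neither 405 nm enzyme assay has a substrate-free digest blank, so any colour change during incubation is read as a change in enzyme activity

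*Combined protocol and SAP*

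**What the plan says.** **Alpha-amylase (Ec 4.1).** Each well takes 50 µL of sample and 100 µL of master solution, which is half assay buffer and half substrate mixture. Products of the various digestion stages are tested, which includes the pepsin stage. Absorbance at 405 nm is read at minute 3 and then every 5 minutes until the samples approach the top standard. The reference is a standard curve: "A calibration curve will be performed with Nitrophenol at concentrations of 4, 8, 12, 16 and 20 nM/well". The standards are not said to contain digest. Ec 4.1 is B × dilution factor / (reaction time × V), where B is the nitrophenol generated. The result is labelled percentage inhibition.

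**Alpha-glucosidase (Ec 4.2).** Samples are prepared in 50 mM phosphate at pH 7.0. A 20 µL portion receives 200 µL of a master solution that contains the substrate. At 405 nm, "the initial measurement (T-initial) will be read and after 20 minutes the final absorbance (T-final) will be taken". Ec 4.2 is (final − initial) / (calibrator − water) × 250 unt/L. The only blank is a water well: "Abs of the water represents the value of the water at 20 minutes".

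**The material tested.** The general description of the plant says "while the calyx is deep red, fleshy and rich in malic acid", and Table 2.1 lists organic acids at 4000 ± 1000 mg/100 g of calyx. The colour and pH of the drink, its digests and the placebo are not given.

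**Use of the result.** Specific objective 5 concerns inhibition by the digested placebo and treatment beverages. The Expected Results section offers enzyme inhibition as one mechanism for lower glucose and insulin.

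**The concern.** The signal in both assays is yellow p-nitrophenol, and the sample may itself be coloured. Every sample well described receives substrate, so the plan has no well showing what the digest's own absorbance does over the incubation. The calibrator, the water well and the nitrophenol curve contain no digest, so they cannot show it either.

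Subtracting the first reading deals with colour that stays constant. If the colour fades or darkens between the two readings, the change is added to the p-nitrophenol signal and reported as enzyme activity. A second possibility is that p-nitrophenol absorbs less at 405 nm when the well is more acidic than the standards.

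At stake is the comparison of hibiscus with placebo in objective 5. If the two digests differ in colour stability or acid load, they can differ in apparent activity without any effect on the enzyme. Adding enzyme controls that contain no digest would not reveal this.

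**Working it through.** The plan states no expected absorbance, pH or effect size for these assays, so there is no figure of its own to reproduce. The check is algebra on the two equations, followed by sensitivity ranges under declared assumptions.

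**1. Constant colour cancels in Ec 4.2.** Assume a true rise of 0.30 and calibrator minus water of 0.50. The result is 0.30/0.50 × 250 = 150 unt/L. Adding 0.40 to both readings leaves the difference, and the result, unchanged.

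**2. Changing colour does not cancel.** With drift d, Ec 4.2 gives (true rise + d)/(calibrator − water) × 250. The error is d/(calibrator − water) × 250, and the relative error is d/(true rise). For an assumed fade of 0.03 and calibrator minus water of 0.50:
- True rise 0.1: 50 becomes 35 unt/L, a 30% apparent loss.
- True rise 0.3: 150 becomes 135 unt/L, a 10% apparent loss.
- True rise 0.6: 300 becomes 285 unt/L, a 5% apparent loss.

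Over a wider assumed range, the error runs from 0.02/1.5 × 250 = 3.3 to 0.10/0.5 × 250 = 50 unt/L. Darkening would act in the opposite direction.

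**3. Alpha-amylase.** The section does not write out how B is obtained from the readings. I take it as the rise in absorbance since minute 3, read off the curve, which is the reading most favourable to the plan. A drift d then shifts B by d divided by the slope of the curve. There is no fixed end time, so the time over which colour can drift is not fixed either.

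**4. Direction in Ec 4.1.** The printed formula is proportional to B. With assumed dilution factor 1, time 20 min and V = 50 µL, B = 10 gives 10/(20 × 50) = 0.010, and B = 5 gives 0.005. A lost signal therefore lowers the printed I%, although it means lower measured activity.

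**5. Low pH, if it occurs.** The coloured (ionised) fraction of p-nitrophenol is 1/(1 + 10^(pKa − pH)), with pKa assumed to be 7.0–7.2. For pKa 7.15 it is 0.415 at pH 7.0 and 0.309 at pH 6.8, a loss of 25.5%. Across the pKa range, the loss relative to pH 7.0 is 23–26% at pH 6.8, 52–57% at pH 6.5 and 82–85% at pH 6.0.

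**6. How exposed each assay is to low pH.**
- Alpha-amylase: the sample is at most 50/150 = 33% of the well, less if the digest is diluted (Ec 4.1 has a dilution factor). No pH adjustment is stated. The well also holds 50 µL of assay buffer of unstated pH.
- Alpha-glucosidase: the sample is 20/220 = 9% of the well and is already in 50 mM phosphate at pH 7.0. With phosphate pKa assumed to be 6.8–7.2 and p-nitrophenol pKa 7.15, an acid load of 2 mM in that buffer gives pH 6.93 (about 10% loss). A load of 5 mM gives about 6.8 (23–25%), and 10 mM gives about 6.6 (42–51%). These figures apply before the 200 µL of master solution is added, which would reduce the effect further.

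**The case against.** **The kits may already include a blank.** Both assays follow manufacturers' specifications that the protocol does not reproduce, and the digestion is adapted from a cited method. A blank or a pH adjustment may therefore be made at the bench. This stands: a reader might infer that no blank will be run, and the text does not show that. What it shows is that the wells and equations are written out and that neither equation has a place for a blank. A blank that was run would not enter the result as specified.

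**The pH route is partly closed.** A reader might infer that acidity distorts both assays, with losses above 80%. The documents do not support that. The alpha-glucosidase samples are buffered at pH 7.0 and diluted into the well, which largely mitigates the effect there. For alpha-amylase the route is more open, but no document gives a well pH, so a loss of that size is only what pH 6.0 would produce if it were reached.

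**Bias towards hibiscus is not shown.** A reader might infer that the error falls mainly on hibiscus wells and makes the product look inhibitory. The red colour and acid are documented for the raw calyx only. A placebo matched on both would offset the bias, and the trial is single-blind, so some matching is plausible. Some drift may also occur before the first reading. All of this stands as uncertainty. It does not remove the gap, because matching is not stated.

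**Lost signal is not printed as inhibition.** Ec 4.2 reports activity, and Ec 4.1 would report a lower I%. Neither contains an uninhibited reference. This also stands: inhibition would be the analyst's inference from lower activity, and the label on Ec 4.1 needs its own correction.

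**Conclusion.** The concern holds in a limited form. As written, neither assay has a substrate-free digest blank in its wells or its equation, so colour change during incubation is confounded with enzyme activity. Whether the placebo cancels this cannot be judged from the documents. Reduced p-nitrophenol signal at low pH is a possible further bias, mainly for alpha-amylase.

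The size cannot be computed from the documents. Every absorbance, acid load, pH and pKa used here is an assumption. The illustrative range is 5–30% apparent loss of activity for a fade of 0.03 on true rises of 0.6 down to 0.1. The documents establish neither the direction of any drift nor a bias specific to hibiscus. The point is a cheap improvement to the in vitro comparison in objective 5; it does not affect the clinical measurements.

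**What to change.** 1. For each hibiscus and placebo digest, at each digestion stage, run one well with digest and buffer but no substrate, read at the same times as the sample well.
2. In Ec 4.2, replace the numerator by (final − initial) of the sample minus (final − initial) of its blank. In Ec 4.1, derive B from the same corrected change. If the blank drifts as the sample does, this removes d exactly.
3. For alpha-amylase, either state that the digest is brought to assay pH and record the check, or add one digest well spiked with a known amount of p-nitrophenol and divide B by the fraction recovered.
4. State whether the placebo is matched to the hibiscus drink for colour and acid.
5. Separately, correct the percentage-inhibition label on Ec 4.1, which as printed rises with the nitrophenol formed.

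The cost is one extra well per digest for alpha-glucosidase and one or two for alpha-amylase, on plates already being run, plus one added term in each equation and a recovery divisor in Ec 4.1 if the spiked well is used.
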